Specific Aim #2: To demonstrate that 10 sessions of 40 Hz tACS stimulation decreases amyloid levels on PET imaging in patients with mild AD.

We hypothesize that 40 Hz tACS will result in a significant decrease in amyloid burden in the stimulated area.

Specific Aim #3: To demonstrate that 10 sessions of 40 Hz tACS stimulation improve resting-state EEG background activity, EEG connectivity, and performance on cognitive testing.

We hypothesize that 40 Hz tACS will result in a normalization of brain activity with increased high frequency (gamma) EEG activity and increased brain network connectivity, and that these changes will be associated with an improvement in memory and general cognitive function.

Exploratory Aim 1: As an exploratory aim, we will analyze the impact of APOE (Apolipoprotein E) and BDNF (Brain Derived Neurotrophic Factor) polymorphisms on individual response to tACS (i.e. change in amyloid level and/or gamma EEG spectral power), as measured via EEG and cognitive testing. Such information will be derived via saliva samples.

Exploratory Aim 2: The response to non-invasive brain stimulation might be related to intrinsic brain properties such as brain plasticity and connectivity levels (Freitas, Farzan, & Pascual-Leone, 2013). We will collect information on plasticity levels via a combined TMS and EEG recording session; responsiveness to tACS will be assessed via a combined tACS-EEG session.

B2. SIGNIFICANCE AND BACKGROUND FOR THE STUDY

Histopathologically, AD is characterized by diffuse amyloid- β (A β) plaques and phosphorylated tau (p-tau) deposition in neurofibrillary tangles, as well as widespread neurodegeneration. Recent PET imaging studies suggest that progressive amyloid deposition can begin up to 20 years before the onset of clinical symptoms and stabilizes around the time that clinical symptoms begin to be prominent (C. R. Jack et al., 2013; C.R. Jack Jr. et al., 2010); that tau is isolated to the lateral temporal lobes without amyloid, and spreads outside the lateral temporal lobes in patients with amyloid; and that neurodegeneration and clinical symptoms are correlated with the spread of tau (Pontecorvo et al., 2017). Consequently, the evidence suggests that both amyloid and tau play a critical role in AD pathogenesis, and interventions that reliably and safely decrease the intracerebral burden of amyloid or tau could potentially be of marked clinical importance.

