- Cognitive Evaluation that includes the MMSE, NACC-UDS questionnaires and cognitive assessments completed at baseline, RAVLT, ADAS-Cog, and CGIC.
- Repeat baseline UDS questionnaires
- PET Imaging – A follow-up PET scan will be obtained to assess the change in amyloid burden in the stimulated target region
- fMRI
- Lumbar puncture (optional)
- Blood draw
- TMS-EEG plasticity assessment
- tACS-EEG with cognitive tasks
- Adverse event review and follow-up
- Review of medications and changes in medical history
- At the completion of the study, subjects will be queried about their overall experience with the study using the Participant Experience Assessment

It is possible that the follow-up visit will be conducted over 4-5 days due to availability of the PET scanner and resource availability.

If participants have plasticity measures or neuropsychological testing from a prior study in the B-A Center, those may be compared to the measures obtained in this study and/or used in place of the testing in this study.

Telephone Follow-up After (1 month and 3 months after completion of visit 18)

The following will occur via telephone call at two time points, approximately 1 month and 3 months after the participant completes the in-person follow-up visits. for assessment of any longer term changes:

Measures that were collected during prior visits will be completed via telephone:

- Telephone version of MoCA completed with study participant
- CGIC to be completed with study participant and study partner
- Activities of Daily Living Inventory (ADL) –(the number of questions in this may be reduced)

For study participants who already completed the study we plan to complete the telephone follow-up retroactively. If the participant has already passed the 1 month follow-up mark, but not the 3 month mark we plan to call them at two time marks-- immediately and at the 3 month mark. If the participant has already passed both the 1 month and 3 month marks, we plan to complete the follow-up assessment with them at one time mark, following up with them as soon as possible.

Methods

Cognitive Measures

Alzheimer's Disease Assessment Scale (ADAS-Cog):

The ADAS-Cog is a standardized neuropsychological assessment that measures the severity of symptoms of Alzheimer's Disease in 11 different domains. The tasks assess the domains of language, praxis, memory, attention and executive function.

Alzheimer's Disease Cooperative Group Study Clinical Global Impression of Change (CGIC):

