can slide into the scanner. Subjects will be handed the emergency button which they can squeeze at any point during the procedure to inform the investigators if they have a question, are feeling uncomfortable, or are in distress. The subject's head will be carefully positioned and foam-padded cushions will be placed on either side of their head in order to prevent movement during the scanning session. The subject will receive earplugs to wear during the entire scanning session in order to minimize the noise of the scanning machine. The subject will then undergo a series of MRI scans of the brain. Structural images will be acquired followed by resting-state functional MRI scans. Total scan time will be about 50 min.

The MRI done in this study is for research purposes only. It will not be read by a radiologist. If there are incidental findings noted on the MRI, the subject will be notified and advised to see their primary care provider for a diagnostic MRI.

For safety reasons, participants whose abdomen, shoulder, or hip circumference is greater than 180cm may need to be excluded from the study.

PET

An amyloid PET scan will be conducted at baseline. A follow-up PET scan will be obtained after the completion of the tACS sessions. PET imaging with Florbetapir-[18]F injection will be performed on BIDMC's Siemens Biograph m64 multidimensional helical PET-CT Scanner. A 10 minute emission scan, acquired with a 128 x 128 matrix (zoom 2) in 1 x 10min frames, will be obtained 30-50 minutes after intravenous injection of 10 mCi (370 Mbq) of Florbetapir F18 (or Florbetaben).

The follow-up PET imaging to be done in this study is the equivalent of a clinical PET study using a ligand that is FDA approved for assessing A β burden. This ligand is the same as the ligand used in the PET obtained prior to enrollment. The scan will be read by a nuclear medicine physician and a report will be prepared.

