tACS involves the administration of low-amplitude (< 2mA) sinusoidal electrical currents via scalp electrodes. Current will be applied in the gamma frequency (40 Hz) range to the regions of tracer uptake on the amyloid PET scan on a case-by-case basis. Although tACS is usually administered via bipolar montages using two large electrodes, such montages have poor spatial specificity. Our group has been at the forefront of efforts using multifocal (multielectrode) montages that can deliver higher amplitude and more spatially specific stimulation patterns (Ruffini, Fox, Ripolles, Miranda, & Pascual-Leone, 2014). Consequently, stimulation will be applied to the target region with maximum amyloid levels using individualized multifocal (multielectrode) montages to maximize the induced electrical current in the target region.

Stimulation will be slowly ramped up/down at the beginning/end of each stimulation session to minimize skin sensation. tACS can elicit phosphenes - a sensation of light caused by excitation of the retina by mechanical or electrical means rather than by light. Participants will be queried each day at the end of the visit to see if they experienced phosphenes. They will be informed that this may happen and will be informed that they are free to ask to stop participation if the phosphenes bother them. We anticipate that a low percent of participants will experience this sensation (10%).

B. Statistical Considerations

Sample Size Justification: Given the intrinsic difficulties in the care of AD patients and the commitment required by the multi-day tACS intervention, we expect an attrition rate higher than 20%, potentially close to 30%. We will compare individual changes in amyloid according to the aforementioned SUVR threshold. In order to get valuable pilot data about changes in PET markers, we aim to recruit up to 20 participants to account for attrition with 10 expected to enroll in the study. This would allow for a final sample of 5/6 fully characterized participants who will complete the tACS

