intervention as well as pre-post multimodal evaluation. As for the quantification of changes in amyloid load, we will compare individual *relative standard uptake values* (SUVR) before and after tACS, according to established threshold values. PET Amyloid levels across brain regions will be quantified using standard uptake values normalized to uptake in the cerebellum (SUVR; (Lopresti et al., 2005)). Studies have suggested that the test-retest reliability of amyloid-PET measurement is high, with an intraclass correlation of 0.99, and a relative measurement error of 3% (C. R. Jack et al., 2013). Subjects will be defined as amyloid positive if the global (across all regions) cortical to cerebellar SUV ratio is greater than or equal to 1.6 (Clifford R. Jack et al., 2008). The annual rate of change in the global and regional amyloid ratio varies as a function of patient clinical status and baseline SUVR, but is generally either nonsignificant or small but positive, typically on the order of 0.05 units/yr, and asymptotes in patients with cognitive deficits and high amyloid levels (C. R. Jack et al., 2013; Clifford R. Jack et al., 2009; Villain et al., 2012; Villemagne et al., 2013), suggesting that major changes are unlikely over the short time period between baseline and post-intervention testing. Furthermore, significant decreases in amyloid (> 0.05 units/yr) are rare, particularly in patients with MCI/AD (C. R. Jack et al., 2013), suggesting that decreases above this magnitude would represent a reliable measure of tACS effect. Changes in SUVR will be evaluated by looking at individual trajectories of amyloid change (i.e. decrease in amyloid load or slowing of amyloid build-up) exceeding the threshold.

Data Analysis:

Changes in EEG metrics (e.g. gamma spectral power), amyloid beta levels, clinical and cognitive scores, as well as brain plasticity levels, will be measured using paired-sample t-test statistics, by applying a p.value < 0.05 . Details about computation EEG-based measures are described below.

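### An SUVR fall above 0.05 lies within the plan's own measurement error. In the maximum-amyloid target, a fall is also expected by regression to the mean wherever one scan both sets the target and gives the pre-tACS value.

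*Combined protocol and SAP*

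**What the plan says.** **Target and outcome.** Section B3.A, tACS (Starstim Device), states that "stimulation will be applied to the target region with maximum amyloid levels using individualized multifocal (multielectrode) montages". The Follow Up Visit section states: "A follow-up PET scan will be obtained to assess the change in amyloid burden in the stimulated target region". Specific Aim #2 in B1 hypothesises that "40 Hz tACS will result in a significant decrease in amyloid burden in the stimulated area". The Overview in B3.A gives every subject the active course, so there is no concurrent control for it.

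**Analysis.** B3.B, Data Analysis, says that changes in "amyloid beta levels, clinical and cognitive scores, as well as brain plasticity levels, will be measured using paired-sample t-test statistics", at p < 0.05. It does not name the region for the amyloid test. B3.B expects 5 or 6 fully characterised completers.

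**Threshold.** B3.B reports an intraclass correlation of 0.99 and "a relative measurement error of 3" per cent. It notes that natural decreases beyond 0.05 units per year are rare, and concludes that "decreases above this magnitude would represent a reliable measure of tACS effect". Individual trajectories are then to be judged against that threshold. Regional amyloid is "quantified using standard uptake values normalized to uptake in the cerebellum", and positivity is a global ratio of at least 1.6.

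**Which scan does what.** The PET section says "An amyloid PET scan will be conducted at baseline", without condition, and also refers to a scan before enrolment. Study Design makes the baseline scan conditional on there being no earlier one. The PET section and B6 Recruitment allow earlier scans to be used. The visit schedule shows one screening and one follow-up scan, while B5 counts three. No section says which scan sets the target and which supplies the pre-tACS SUVR. The targeting rule also varies: the Overview and Study Design describe it more broadly than a single maximum.

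**The concern.** There are two separate problems.

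**The threshold.** A difference between two scans carries the error of both. If 3% of SUVR is about 0.05, a fall of 0.05 is an ordinary result of rescanning. The plan would then count some participants as showing a tACS effect on noise alone. The 0.05 is also an annual rate from natural history, whereas the study will look at a raw difference between two scans.

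**The target.** A region picked because its reading is highest is, on average, picked partly because its error on that scan was positive. If the same reading is the pre-tACS value, the next one tends to be lower with no treatment effect. The bias runs in the direction of the Aim 2 hypothesis, and a one-sample comparison with zero has nothing to set against it.

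B1 names follow-on studies meant to show that the amyloid reduction is sustained. A fall misread here would shape them.

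**Working it through.** **1. Threshold (needs no assumption about targeting)**

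Inputs from B3.B: error 3%, threshold 0.05, positivity cut-off 1.6. SUVR of 1.8 and 2.0 are assumed for illustration. The plan does not say whether 3% is the error of one scan or the SD of a test-retest difference, so both are shown. The reported ICC is compatible with either only through the spread between people: 0.048 × √(0.99/0.01) ≈ 0.48. A high ICC therefore does not show that 0.05 exceeds the error.

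P(fall > 0.05 with no effect) = Φ(−0.05 / SD of the difference). At least one of six: 1 − (1 − p)^6.

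| SUVR | SD of difference, per-scan reading (0.03 × SUVR × √2) | p | ≥1 of 6 | SD if 3% is already the difference | p | ≥1 of 6 |
|---|---|---|---|---|---|---|
| 1.6 | 0.068 | 23% | 79% | 0.048 | 15% | 62% |
| 1.8 | 0.076 | 26% | 83% | 0.054 | 18% | 69% |
| 2.0 | 0.085 | 28% | 86% | 0.060 | 20% | 74% |

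A 95% limit for a difference at SUVR 1.6 is 1.96 × √2 × 0.048 = 0.13, or 1.96 × 0.048 = 0.09 on the second reading.

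**2. Target selection, one scan in both roles**

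Assumptions not in the documents: 10 regions, mean SUVR 1.8, per-scan regional error 0.03 × 1.8 = 0.054, true between-region SD (τ) of 0.05, 0.10 or 0.20, six participants, no tACS effect and no drift. The test is taken as two-sided, so the nominal rate of a false significant decrease is 2.5%.

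Expected fall = 1.539 × σ² / √(τ² + σ²). Here 1.539 is the expected maximum of 10 standard normals and σ² is the region-specific part of the error variance. With independent error and τ = 0.05: 1.539 × 0.002916 / √(0.0025 + 0.002916) = 0.061. False-decrease rates are simulated.

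| Error variance shared across regions | Mean fall (τ = 0.05 / 0.10 / 0.20) | False decrease, single highest region | False decrease, mean of top 3 |
|---|---|---|---|
| None | 0.061 / 0.039 / 0.022 | 41 / 19 / 8% | 53 / 25 / 10% |
| Half | 0.036 / 0.021 / 0.011 | 16 / 8 / 5% | 13 / 7 / 4% |
| 80% | 0.016 / 0.009 / 0.004 | 6 / 4 / 3% | 5 / 4 / 3% |

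The mean-fall column is for the single highest region. A separate, independent pre-tACS scan gives a fall of 0.000 and a rate of 2.5%. If only three of six participants are same-scan, the independent-error row (single highest region) becomes 11 / 7 / 5%. With close regions (τ = 0.05), selection raises the chance of an individual fall above 0.05 from 26% to 33% (80% shared), 42% (half) or 56% (none).

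**3. Comparators**

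- *Target minus unstimulated regions.* Errors across all regions average zero, so the nine unselected regions are biased the other way by one ninth. The contrast therefore moves by 10/9 of the fall: with independent error, 0.061 × 10/9 = 0.068 down to 0.022 × 10/9 = 0.024. It does not remove the bias.
- *Global SUVR.* It avoids target selection, but participants must qualify at 1.6 or more. If the qualifying scan is also the pre-tACS scan, the expected fall is σ²/S × φ(z)/(1 − Φ(z)), with S = √(between-person variance + σ²) and z = (1.6 − mean)/S. For σ = 0.054, assumed population means of 1.6-1.8 and SDs of 0.1-0.54, this is about 0.002 to 0.02.
- *Dilution.* A true fall of 0.10 in one of 10 regions moves the global mean by 0.01.

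**4. Drift**

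The stated rise of 0.05 per year gives 0.05 × 5/52 ≈ 0.005 over an assumed five weeks, and lowers the independent-error rates (single highest region) only to 36 / 15 / 6.5%. If the scan used for both roles is a year old (+0.05), they become 5 / 1.2 / 0.3%: drift then outweighs the bias and could mask a real fall of that size.

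**The case against.** The strongest case against is that the selection bias needs several conditions together: one scan in both roles, a rule close to picking the maximum, a t-test on the target region, and region-specific error that is not small beside the true spread between regions. The documents fully settle none of these. All regions share the cerebellar denominator, so much of the error may be common. A dominant region also shrinks the effect: with a between-region SD of 0.48, the fall is at most 0.009 and the false rate 2.8-4.3%. This is a safety and feasibility pilot looking for an initial signal.

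Most of that stands as a limit on size. It does not remove the point. Participants with only suspected amyloid are first scanned at screening, and the schedule shows one pre-treatment scan. For them one scan is likely to play both roles, though the count of three scans in B5 leaves this open.

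On the threshold, the plan can reply that it relies on the observed rarity of such decreases. That evidence is an annual rate. It does not show that a raw two-scan difference of 0.05 exceeds the error the plan itself quotes.

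A reader might infer that the t-test has a 41% false-positive rate, or that any fall in the target would be an artefact. The documents support neither: 41% belongs to one set of assumed inputs, and top-three averaging gives 53% under the same ones. A reader might also take global SUVR as an unselected, bias-free comparator, but the 1.6 entry requirement rules that out.

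**Conclusion.** The threshold statement is not supported by the plan's own error figure. With no effect, 15-28% of individuals at SUVR 1.6-2.0 would cross 0.05, and 62-86% of six-person samples would contain at least one. This rests only on normal error and on which reading of 3% applies.

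The selection bias is real in direction for any same-scan participant with region-specific error, and a single-arm paired test cannot separate it from tACS. Its size is not determined by the documents. Under the assumed inputs the false significant-decrease rate runs from near nominal (3-6% with 80% of error shared) to about 40-50% with independent error and close regions. These are illustrations, not bounds. The bias does not apply to participants whose pre-tACS value comes from a separate, independent scan. Global SUVR avoids it but carries a smaller regression effect of its own where the qualifying scan is also the pre-tACS scan.

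The plan should be changed on both counts; confidence in the selection part is medium.

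**What to change.** 1. **Threshold.** Replace the B3.B statement. Do not read an individual fall above 0.05 as a reliable tACS effect. Judge individual falls against a limit derived from the error of a difference, for example 1.96 × √2 × 3% of SUVR (about 0.13 at SUVR 1.6), or about 0.09 if 3% is already the SD of the difference. State which reading is used.
2. **Analysis and reporting.** Keep Aim 2 and the t-test, and name the analysed region. Report global SUVR change and unstimulated regions beside the target result. State how many participants are same-scan, that their target-region fall includes regression to the mean, that a target-minus-unstimulated contrast does not remove it, and that global SUVR dilutes a focal effect.
3. **Scan roles.** Reconcile B3.A (Overview, Study Design, PET, tACS), the visit schedule, B5 PET and B6 Recruitment on which scan sets the target and which gives the pre-tACS value. Where two pre-tACS scans with the same tracer and method exist, add a sensitivity analysis that uses the non-targeting scan as the pre-tACS value. Report the interval, because drift over a long gap can offset or mask an effect.

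**Cost.** SAP wording and a few descriptive results, with no new scans and no change to treatment. The price is a more cautious amyloid conclusion and fewer individual responders: at SUVR 1.6 on the per-scan reading, a true fall of 0.10 would pass the 0.13 limit only Φ((0.100 − 0.133)/0.068) ≈ 31% of the time. The group t-test is untouched. With a separate pre-tACS scan at SUVR 1.8, its power for a true 0.10 fall is 60% with five participants and 73% with six.

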The study will be conducted at BIDMC, at the Berenson-Allen Center for Noninvasive Brain Stimulation and in the Clinical Research Center. We aim to study 10 individuals with AD with evidence of increased cerebral amyloid burden on amyloid PET imaging. Up to 20 participants will be enrolled to account for attrition. Each subject's participation in the study will consist of up to 18 visits: 4-5 days for screening/baseline procedures as described below (these baseline assessments may happen over 4-5 days to accommodate scheduling and the participant), 10 tACS study visits, and 4-5 days for follow-up assessments. Subjects will undergo baseline cognitive assessment, structural and functional MRI characterization, resting-state EEG measurement and amyloid PET scan (if not previously obtained). Additionally, patients will undergo a TMS-EEG and a tACS-EEG recording session to assess brain plasticity levels and identify markers of response to stimulation. All subjects will subsequently undergo 10 sessions of gamma-frequency (40 Hz) tACS. The stimulation sites will be identified on a case-by-case basis taking into account the overall distribution of amyloid- β as evidenced by the amyloid PET scan. Subjects will take a standardized adverse effect questionnaire before and after each session to demonstrate safety and tolerability (Fertonani et al., 2015). At the end of the 10 sessions, subjects will then repeat the baseline assessments, followed by repeat amyloid PET imaging to assess for changes in amyloid burden.

Procedures

Screening and Baseline Visit (Visits 1-4)

During the screening and baseline visit, participants will provide informed consent and complete the following procedures:

- Neurological exam*
- Demographic review*
- Review of medical, psychiatric and medication history, including review of diagnosis*
- tACS and TMS safety questionnaires*
- MMSE*
- The Clinical Dementia Rating (CDR) scale to assess severity of dementia*
- Inclusion/Exclusion criteria review*
- MRI screening questionnaire
- Alzheimer's Disease Assessment Scale Cognitive Subscale (ADAS-Cog)
- Baseline Clinical Global Impression of Change (CGIC)

- National Alzheimer's Coordinating Center's Uniform Data Set (NACC-UDS) questionnaires: Activities of Daily Living Inventory (ADL); Geriatric Depression Scale (GDS); Functional Assessment Questionnaire (FAQ)

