The RAVLT consists of a list of 15 unrelated words repeated after 5 trials and are asked to repeat. Another list of 15 unrelated words is given and the participant is then asked to repeat the original list of words immediately and then after 30 minutes. This is an assessment of short-term auditory-verbal memory, rate of learning, learning strategies, interference, presence of confabulation or confusion in memory process, retention and differences between learning and retrieval.

Wechsler Test of Adult Reading (WTAR) – ONLY completed at baseline:

The WTAR is a neuropsychological assessment used to assess a pre-morbid level of intellectual functioning prior to the onset of an illness or disease. It consists of a series of irregularly spelled words that are presented to the subject while prompting them to pronounce the word.

Additional Measurement Instruments:

Handedness Questionnaire – ONLY completed at baseline:

The handedness questionnaire is an assessment of hand dominance, based on the Edinburgh Handedness Inventory (Oldfield, 1971).

National Alzheimer's Coordinating Center's Uniform Data Set (NACC-UDS) questionnaires:

The following questionnaires will be collected: Activities of Daily Living Inventory (ADL); Geriatric Depression Scale (GDS); Functional Assessment Questionnaire (FAQ) - Please see attached.

MRI

MRI will be performed on BIDMC's 3T GE MR750 MRI Scanner. A high resolution T1-weighted structural scan will be obtained from the scanner. The MRI will be used in combination with the PET images to define the stimulation targets. Additional standard MR protocols to assess resting-state functional connectivity, cortical metabolism, or white-matter integrity, may be included if time allows.

All MRI imaging will be conducted at the Beth Israel Deaconess Center Medical (East campus). The subject will be brought into the scanner room and instructed to lie down on a foam-padded table that

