Participants will be informed of their baseline amyloid imaging results as the scan must be positive to be included in the study. The study investigator will inform the participant if the scan was positive or negative and will be clear with the participant that this scan was collected for a research study. If participants would like to understand how their results relate to their diagnosis or care, they can opt to have the results shared with their provider. The scans are all collected and read in the same manner that they would be if done clinically. If participants are in agreement that they would like to share the scan results with their provider, the study team will work with them to provide this information to their care provider. If they do not have a provider who is comfortable with relating the results to the subject's care or if they do not have a provider, the study team will work with them to arrange an appointment in the Cognitive Neurology Unit.

If patients have had a clinical or research amyloid PET at BIDMC, we may use these results as a measure of amyloid progression.. If patients have had a clinical PET at an outside hospital, we may ask them to obtain a copy to compare with the current study.

TMS – EEG: Brain plasticity and responsiveness to stimulation

The TMS-EEG measures will be collected at baseline and then again following the 10 day tACS intervention to assess for changes in neural plasticity. Subjects will be set up in a chair with an EEG cap and with EMG electrodes placed on the right hand for collection of motor evoked potentials (MEPs) during stimulation over the left primary motor cortex (M1). The EEG cap and EMG electrodes will remain in place throughout the TMS session. EEG will be recorded throughout the session.

Participants will be provided ear protection to be worn throughout the session. TMS specific adverse effect review will be reviewed prior to and at the end of the session.

- **Baseline Resting State EEG and artifact recording:**

Baseline resting state EEG and artifact recordings will be obtained with the eyes open for five minutes and then eyes closed for five minutes. Subjects will be asked to briefly move their eyes, clench their jaws, and tense their foreheads so that the EEG artifacts associated with these movements can be recorded and similar artifacts removed from the remaining EEG recordings.

- **Assessment of Motor Threshold:**

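### Where one pre-treatment PET both picks the high-amyloid target and supplies its baseline SUVR, some fall in the target is expected without any tACS effect, and the single-arm analysis cannot tell the two apart

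*Combined protocol and SAP*

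**What the plan says.** **Choice of target.** B3.A, tACS (Starstim Device), first directs current to regions of tracer uptake, case by case, and then says "stimulation will be applied to the target region with maximum amyloid levels". B3.A, MRI, adds: "The MRI will be used in combination with the PET images to define the stimulation targets". The Study Design text is looser and refers to the overall amyloid distribution.

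**Endpoint.** Specific Aim #2 hypothesises that "40 Hz tACS will result in a significant decrease in amyloid burden in the stimulated area". The Follow Up Visit section says the repeat PET is done "to assess the change in amyloid burden in the stimulated target region".

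**Analysis.** In B3.B, amyloid levels are "quantified using standard uptake values normalized to uptake in the cerebellum". Changes are tested by paired t-test at 0.05. Individual falls are also set against a threshold of 0.05 SUVR units (written per year), and falls beyond it are described as dependable evidence of a tACS effect.

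**Scans before treatment.** The Study Design lists an "amyloid PET scan (if not previously obtained") among the baseline procedures, and the visit schedule shows one PET before and one after treatment. Other passages allow two pre-treatment scans. The PET section says of the follow-up ligand, "This ligand is the same as the ligand used in the PET obtained prior to enrollment", and of earlier scans, "If patients have had a clinical PET at an outside hospital, we may ask them to obtain a copy". B5, PET, counts three scans. The plan does not say which scan sets the target and which is the baseline.

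**Control.** Under B3.A, Overview, every subject receives active tACS.

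**The concern.** A region chosen because it reads high on an error-prone scan will, on average, carry a positive error on that scan. If that reading is also the baseline, the repeat scan brings a fresh error with mean zero and the region appears to fall. This is regression to the mean, and it runs in the direction of the Aim 2 hypothesis.

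The plan's defence of its threshold is that reliability is high and natural decreases are rare. That argument concerns unselected measurements and does not cover a region picked for its high reading. The plan mentions neither this selection nor a separate baseline scan. With 5 or 6 completers, even a modest one-sided shift could colour the amyloid signal that, according to B1, later studies are meant to extend.

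**Working it through.** **Inputs from B3.B.** Relative measurement error is 3%, the positivity cut-off is SUVR 1.6, the threshold is 0.05 and there are 5 or 6 completers. The plan states no power or detectable change to reproduce. Its completer figure follows only roughly from its attrition: 10 × (1 − 0.30) = 7, against 5/6. I use n = 6.

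**Assumed, not in the documents.** There are 8 candidate regions with normal, exchangeable errors. The true between-region SD within a patient (τ) is 0.05 to 0.478; the upper value is the SD that the plan's ICC of 0.99 would imply if it applied to regions. The share of error variance specific to a region is 20%, 50% or 100%, since error in the cerebellar denominator is common to all regions and hardly changes their ranking. The 3% is taken as per-scan error, the t-test as two-sided, and 0.05 as an absolute change between scans, which is the reading kinder to the plan.

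**Scan noise alone.** Per-scan error is 0.03 × 1.6 = 0.048. The SD of a scan-to-scan difference is 0.048 × √2 = 0.068. The chance that an unchanged, unselected region falls by more than 0.05 is P(Z > 0.05/0.068) = 23%.

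**Expected fall from selection.** With v the region-specific error variance,

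fall = c × v / √(τ² + v),

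where c is the expected maximum of 8 standard normals, 1.42.

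- Middle case (50%, τ = 0.10): v = 0.5 × 0.048² = 0.00115, so the fall is 1.42 × 0.00115 / 0.106 = 0.0155. Simulation gives 0.0155.
- Low end (20%, τ = 0.478): v = 0.00046, so the fall is 1.42 × 0.00046 / 0.478 = 0.0014.
- High end (100%, τ = 0.05): v = 0.0023, so the fall is 1.42 × 0.0023 / 0.069 = 0.047.

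**Simulation with no treatment effect** (40,000 trials per setting, single maximum region). A significant fall should occur in 2.5% of trials.

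| Region-specific share | τ | Mean fall | Significant fall | Unchanged patients past 0.05 |
|---|---|---|---|---|
| 20% | 0.05 | 0.012 | 5% | 29% |
| 20% | 0.20 | 0.003 | 3% | 25% |
| 50% | 0.10 | 0.016 | 7% | 30% |
| 50% | 0.30 | 0.005 | 4% | 26% |
| 100% | 0.10 | 0.029 | 15% | 38% |
| 100% | 0.05 | 0.047 | 32% | 48% |

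With τ of 0.30 to 0.478 and 20-50% region-specific error, the fall is about 0.001-0.006 and the rate 2.7-3.6%.

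**Variations, τ 0.05 to 0.20.**
- Averaging the top 4 of 8 regions gives a fall of 0.002-0.024 and a rate of 3-31%.
- If 3% is the SD of the scan-rescan difference (0.048/√2 = 0.034 per scan), the single-maximum fall is 0.002-0.027 and the rate 3-22%.
- If 3 of 6 patients are targeted on an earlier scan, the cohort fall is 0.002-0.024 and the rate 3-9%.
- If all 6 are, the fall is 0.000 and the rate about 2.5%. Separating the scan roles therefore removes the selection effect, but the 23% from scan noise remains.

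**The case against.** **The effect may be negligible.** This stands as a limit on size. If regions differ widely and most error is shared, the shift is a few thousandths of an SUVR unit. Ordinary scan noise, at 23% of unchanged patients past the threshold, is then by far the larger weakness of the 0.05 rule. A reader might infer from the 32% and 48% that the Aim 2 test is badly broken. The documents do not support that: those figures need regions that barely differ and an error with no shared part.

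**Targeting is not a strict maximum.** It is case by case and uses MRI and current modelling. Softer selection shrinks the effect, but any preference for high uptake keeps its sign.

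**Some patients may have two pre-treatment scans.** This is true, and the point is confined to those who do not, or whose two scans are not kept to separate roles. A reader might infer that one scan does both jobs for every patient; the PET section and the three-scan count in B5 do not support that.

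**The net change need not be a fall.** If an old scan is the baseline, the accumulation the plan cites (typically about 0.05 per year, levelling off in impaired patients with high amyloid) could offset part or all of the selection fall. The direction is clear for the selection component only.

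**It is a pilot.** B1 speaks of an initial signal and B3.B of pilot data. The plan never calls the target-region test confirmatory, and B3.B does not name target-region SUVR as the tested variable; that link comes from Aim 2 and the Follow Up Visit section. A single-arm pilot is a legitimate choice. What does not survive is the statement that falls above 0.05 can be relied on as a tACS effect.

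**Conclusion.** The point holds for patients in whom one pre-treatment PET both sets the target and supplies its baseline SUVR. Some fall in the target is then expected with no treatment effect, unless all error is shared across regions, and the single-arm analysis cannot separate it from a tACS effect. In these patients the plan's reading of falls above 0.05 is not justified for target-region SUVR.

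The documents fix the direction of the selection effect but not its size, which runs from practically nothing to almost the plan's own threshold. That range rests on the assumed region count, between-region SD, error share and targeting rule, and on reading the 3% as per-scan error. It would be wrong to conclude that an observed fall must be an artefact. The safety and tolerability aim is unaffected. This should be corrected; confidence is medium, because the scan roles are unstated.

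**What to change.** 1. Before session 1, record for each patient which scan set the target and which supplies baseline SUVR, and save the target mask. Saving the mask alone does not remove the effect.
2. Where a usable earlier positive scan and a study baseline scan both exist, take the target from the earlier one and baseline SUVR from the study scan. If the team prefers the current scan for treatment reasons, handle that patient under step 3.
3. For single-scan patients, and for any pooled test that includes them, do not read a target-region p < 0.05 or a fall above 0.05 as evidence of a tACS effect. Report the change descriptively beside global cortical SUVR change, which involves no choice of region. Delete or qualify the B3.B sentence on falls above the threshold.
4. Optionally, show the selection-only fall as a sensitivity range and not as a correction. State the assumed targeting rule and region count, because c is undefined without a rule. Pool the between-region SD across patients, since a per-patient SD from 8 regions overstates the fall by about 12%. Take the 3% both as per-scan error and as the scan-rescan difference, and show region-specific shares of 20%, 50% and 100%.

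**Cost.** One recorded field, a saved mask and some wording, with no added scan, radiation or patients. The target-region test carries less evidential weight, and an earlier targeting scan may be older or from another hospital. Scan noise remains a separate problem.
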